## SPECIFIC AIMS

Alzheimer's disease and related dementias (ADRD) negatively impact millions of Americans with an annual societal cost of more than \$200 million. Currently, half of Americans living with ADRD never receive a diagnosis. For those who do, the diagnosis often occurs two to five years after the onset of symptoms. As stated by the National Institute on Aging (NIA) (RFA-AG-20-051) "*The inability to diagnose and treat cognitive impairment results in prolonged and expensive medical care*" and "*early detection could help persons with dementia and their care partners plan for the future*". Furthermore, if the development of disease modifying therapeutics for ADRD is successful, this may require the use of such therapeutics at a very early stage of ADRD. However, the current approaches of using cognitive tests or biomarkers for early detection of ADRD are not scalable due to their low acceptance, their invasive nature, their cost, or their lack of accessibility in rural or underserved areas. Thus, the NIA called out for the development of low cost, effective, and scalable approaches for early detection of ADRD (RFA-AG-20-051).

Over the past five years, two interdisciplinary scientific teams led by Drs. [name], [name], and [name] (MPI on this proposal) have developed and tested scalable approaches for the early detection of ADRD. At Indiana University, Drs. [name] and [name] leveraged the widely available electronic health record (EHR) data and advances in Machine Learning algorithms to develop a Passive Digital Marker (PDM) for early detection of ADRD with 80% accuracy for one-year and three-year prediction horizons. At the same time, [name] team developed and tested the Quick Dementia Rating Scale (QDRS) as a practical 2-3 minute patient-reported outcome (PRO) tool, for both early detection and staging of ADRD with 85% accuracy for ADRD diagnosis. If implemented successfully within the current Medicare funded Annual-Wellness Visit (AWV), an integrated approach based on the above two ADRD detection approaches (the PDM and the QDRS) may overcome the current barriers to early ADRD detection in a cost- and time-efficient manner that can be generalized across any primary care practice.

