**D.5. Interventions and Control for the Pragmatic (Phase IV) Trials:** Our interdisciplinary scientific teams developed and tested both the PDM and the QDRS. Drs. [name] and [name] leveraged the widely available EHR data and the advantage of ML to develop the PDM with an approximate 80% accuracy for one-year and three-year prediction horizons. [name] team developed and tested the QDRS as a practical 2-3 minute patient reported outcome (PRO) tool for both early detection and staging of ADRD. Each pragmatic trial will randomize primary care practices into one of three approaches for early detection of ADRD at (1:1:1) ratio. These approaches include the current state of using AWV in primary care (the control group), the incorporation of the PDM into the AWV, and the combination of PDM and QDRS (Passive + QDRS). All of the three approaches will be implemented within the current Medicare funded AWV and will be integrated within the provider clinical encounter to accommodate the clinical flow and data capture and results display needs of the primary care practices. To randomly assign each practice to one of the three screening approaches, we will use a computer-generated randomization scheme.

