For Secondary Hypothesis 2, the analyses will be the same as described for Hypothesis 1 of Aim 2, except that the outcome will be acceptance rates for recommended ADRD diagnostic work-up following positive screen. We hypothesize the acceptance rate will be 44% using AWV alone and 66% with the screening approach that combines AWV + PDM + QDRS.

Potential problems & alternative strategies: Same as those described for Aim 1 above.

**D.8.c. Sample Size & Power:** Calculations were performed with PASS, a comprehensive power and sample size software. All calculations assume two-sided tests and alpha = 0.05. For study 1 (i.e., Aim 1), a sample size of 15 cluster pairs consisting of 400 persons (26.667 persons per cluster) will provide 81% power to compare population values of 75% versus 85% in the outcome of % accuracy of classification. This is based on using nonlinear mixed models to compare two paired (i.e., dependent) proportions. The proportions are considered dependent instead of independent because all three screening approaches for study 1 will be performed in the same sample of 400. This approach was selected because it will increase power by allowing participants to serve as their own controls. Moreover, it is appropriate for a diagnostic validity study to compare methods in the same sample (i.e., method contamination is not an issue). This calculation assumes that participants are recruited from 15 clinics (i.e., clusters) and that the within-pair coefficient of variation (CV) between clusters is .058. The CV was calculated as  $CV = \text{SQRT} (ICC \times (1 - \phi) / \phi)$ , where the intraclass correlation coefficient (ICC) was assumed to be 0.01, and phi is 0.75 (i.e. the proportion of accuracy for one of the standard screening methods). The power will be slightly greater than 81% to detect values of 75% versus 85% in the AUC, based on power for comparing two dependent AUC's, assuming discrete cutoff values, and accounting for a sample inflation factor (IF), where  $IF = [1 + (M - 1) * ICC]$ , M = average number of persons per cluster, and the ICC is 0.01.

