#### **D. 9. Potential problems & alternative strategies**

First, while we expect that adding EHR-based data (the PDM) elements to the QDRS based process of ADRD detection will boost validity from 75% to 85% for AUC or for the overall % accuracy of classification, these gains may be marginal (<10%). Smaller gains would signal a precautionary lesson on the limits of EHRs to detect ADRD as currently designed. Second, given the heterogeneity of EHR data, adding EHR data might actually cause the ADRD detection process to gain validity at the cost of reliability. Given Medicare's growing reliance on EHRs for quality measurement, illuminating such a trade-off would be highly policy-relevant. Third, this work involves two states (Florida and Indiana), which may limit generalizability. However, the diversity of the study population may overcome these limitations. Fourth, the intervention faces barriers, such as stakeholder buy-in, unintended consequences, alert fatigue, and clinical uncertainty. We will overcome these barriers by (1) working closely with the leadership of the primary care practices to ensure stakeholder buy in, (2) leverage the trusted relationship between the patient and her primary care team, (3) the proposed PDM and QDRS will be fully integrated within the AWV and the clinical flow of the primary care practices, and (4) working with Drs. [name] and [name] (their Epic Team) to trouble shoot EHR integration barriers and minimize alert fatigue. Based on our extensive preliminary studies, the combined approach of using the PDM and the QDRS would outperform the current state of using the AWV alone or the integration of the PDM within the AWV clinical flow. Fifth, seamlessly integrating the PDM and QDRS within the AWV clinical workflow with limited disruption can be challenging. The Regenstrief Institute has more than a decade of experience with, and has the technical infrastructure in place for, developing and integrating various CDS within Epic, Cerner, and other EHR vendors across the world (see Facilities & Other Resources). We have also allocated sufficient time between the analysis of Aim 1 and go-live of Aim 2 (see **Timetable**) to make any necessary adjustments. Lastly, we will be monitoring uptake and usage of the CDS intervention using the system logs. If uptake during the go-live period appears problematic, we will be able to revisit training / socializing the new workflow with clinical staff or alter the user interface based on feedback.

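### Aim 1: the 81% power sets the single tool at 75% accuracy, but the plan credits the QDRS alone with 85%, the value planned for the combination, and explains no discount

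*Combined protocol and SAP*

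**What the plan says.** **Power (D.8.c).** The Aim 1 sample "will provide 81% power to compare population values of 75% versus 85% in the outcome of % accuracy of classification". The inputs are given: "All calculations assume two-sided tests and alpha = 0.05"; 15 clusters averaging 26.667 persons; ICC 0.01; and "the within-pair coefficient of variation (CV) between clusters is .058", derived with the single-tool accuracy set at 0.75. A further sentence puts the power for AUC 0.75 v 0.85 slightly above 81%.

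**Hypotheses (Specific Aims, D.8.a).** The combination is expected to reach at least 0.85 and each single tool at least 0.75. Aim 1 Secondary Hypothesis 2 says the combination will have a better AUC than each tool alone.

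**Expected gain (D.9).** Adding EHR-based PDM data to the QDRS process "will boost validity from 75% to 85% for AUC or for the overall % accuracy of classification". D.9 allows that the gain may be under 10 points, and then says: "Smaller gains would signal a precautionary lesson on the limits of EHRs to detect ADRD as currently designed".

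**QDRS performance.** Specific Aims describe the QDRS as a tool "for both early detection and staging of ADRD with 85% accuracy for ADRD diagnosis". A.4 repeats the figure for the QDRS as a patient-reported tool.

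**PDM performance.** D.5 describes the PDM "with an approximate 80% accuracy for one-year and three-year prediction horizons". Table 3 gives the full model (RDNx) 77.43% at one year and 73.50% at three years.

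**The concern.** D.8.c and D.9 start from a single tool at 75% and end with the combination at 85%. For the QDRS, the plan's own starting figure is 85%, so the planned gain over the QDRS is zero. Aim 1 Secondary Hypothesis 2 needs the combination to beat both tools, so the stronger one governs, and on the credited figures that is the QDRS.

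Two things are at stake. First, a reader will take 81% as the power for combined against single tool, whichever tool is meant. Second, D.9 commits in advance to reading a gain below 10 points as a limit of EHR data. If the QDRS performs as credited, a small gain is expected however good the EHR data are, and that reading would be wrong.

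**Working it through.** **Inputs** (all D.8.c unless noted): K = 15 cluster pairs; m = 400/15 = 26.667; two-sided alpha 0.05; c = 0.058, which is √(0.01 × 0.25/0.75) = 0.0577 rounded up. Comparator accuracies come from Specific Aims, A.4, D.5 and Table 3.

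**Step 1. Reproduce the 81%.** Matched-pair cluster formula for two proportions:

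v = [p₀(1−p₀) + p₁(1−p₁)]/m + c²(p₀² + p₁²)

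power = Φ( √[(K−2)(p₁−p₀)²/v] − 1.96 )

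For 0.75 v 0.85: v = (0.1875 + 0.1275)/26.667 + 0.058² × (0.5625 + 0.7225) = 0.01181 + 0.00432 = 0.01614. Then √(13 × 0.01/0.01614) = 2.838, and Φ(2.838 − 1.96) = Φ(0.878) = 81.0%. The plan's figure reproduces.

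**Step 2. Same formula, combination held at 85%.** The range reflects c = 0.058 or c recomputed from ICC 0.01 at the comparator's own accuracy.

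| Comparator | Source | Power |
|---|---|---|
| 73.50% | PDM 3-year, Table 3 | about 90% |
| 75% | D.8.c planning value | 81% |
| 77.43% | PDM 1-year, Table 3 | 58-60% |
| 80% | PDM headline | 31-33% |
| 85% | QDRS, Specific Aims and A.4 | alpha only (2.5% in the favourable direction) |

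**Step 3. Combined accuracy detectable with 80% power.** Solving the same formula for p₁ gives about 0.87 against 77.43%, 0.89 against 80%, and 0.93-0.94 against 85%.

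**Step 4. How far the 80% v 85% result depends on pairing.** A person-level paired (McNemar) calculation uses n = 400/[1 + 25.667 × 0.01] = 400/1.257 = 318, difference d = 0.05 and discordant proportion ψ:

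power = Φ( [d√n − 1.96√ψ]/√(ψ − d²) )

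The plan does not state ψ, so these values are assumptions:

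- ψ = 0.29 (independent errors: 0.80 × 0.15 + 0.20 × 0.85): 38%
- ψ = 0.15: 64%
- ψ = 0.10: 81%
- ψ = 0.07: 92%

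**Step 5. AUC.** The AUC power cannot be reproduced, because neither prevalence nor the correlation between the tools' AUCs is stated. With the Hanley-McNeil variance, n = 318, and assumed prevalence 13-30% and correlation 0.3-0.6, power is 51-97% for 0.75 v 0.85 and 18-51% for 0.80 v 0.85.

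**The case against.** **The PDM figures support 75%.** This stands. Table 3's two values bracket 75%, with mean (77.43 + 73.50)/2 = 75.5%, and at the 3-year value power exceeds the stated 81%. A reader might infer that the planning value contradicts the plan's figures for both tools. The documents do not support that for the PDM, where the rounded 80% is what fits poorly with Table 3.

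**The combination is not capped at 85%.** This stands. Both values are floors, and holding only the combination at its floor makes the gain small. By the Step 2 formula, 80% v 90% has 86-89% power. A 10-point gain over the QDRS is therefore unsupported by the plan's figures, not impossible.

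**A discount could be reasonable.** This also stands. C.5 says the QDRS was first tested as an informant rating, and its patient version was studied in neurology clinics. In Table 5 the patient version agrees less well with the CDR than the informant version (0.740 v 0.826). Study 1 enrols primary care patients without a prior diagnosis. But the plan makes no such argument.

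**The 31-33% is fragile.** It is. Under the either-positive rule in D.8.a, improvements over the PDM can come only from cases the PDM missed. At an assumed 30% prevalence and Table 3's 1-year sensitivity of 76%, those are at most 0.30 × 0.24 = 7.2% of patients. A net 5-point gain then allows at most 2.2% losses, so discordance is at most 9.4% and person-level power at least about 83%. At 40% prevalence the same steps give 9.6% + 4.6% = 14.2% and about 66%.

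**The 81% is for % accuracy, while Aim 1 Secondary Hypothesis 2 is on AUC.** Correct. A reader might infer that the AUC comparison is shown to be underpowered. It is not shown; it cannot be checked without the missing inputs.

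None of these points explains why the QDRS is 85% in one place and 75% in another.

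**Conclusion.** The 81% is correct for 75% v 85% accuracy, but it does not describe the QDRS comparison at the plan's own QDRS figure. With QDRS and combination both at 85%, there is nothing to detect. The conflict lies between Specific Aims and A.4 on one side and D.8.c and D.9 on the other, with no discount stated.

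For the PDM the planning value is broadly consistent with Table 3: about 60% power at the 1-year accuracy and about 90% at the 3-year. Only the 80% headline gives low power, and that result depends on discordance.

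These results assume % accuracy as the endpoint, the combination at exactly 85%, and the matched-pair cluster formula that returns the plan's own figure. The D.9 sentence on smaller gains is unsafe whichever figure is right, because a strong QDRS or low power could produce a small gain. This is a should-fix: it affects a secondary hypothesis, and the design can stay as it is.

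**What to change.** **D.8.c.**

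- Reconcile the two QDRS figures, or give the reason for planning at 75%.
- Say which PDM accuracy applies.
- Replace the single line with power for comparators from 73.5% to 85%.
- State the combined accuracy detectable with 80% power: about 0.87 against 77.4%, 0.89 against 80% and 0.93-0.94 against 85%. Label these as % accuracy under the plan's cluster formula.
- State the prevalence and correlation behind the AUC power.
- Name the hypothesis as Aim 1 Secondary Hypothesis 2, since Aim 2 has one with the same label.

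**D.9.** Replace the sentence on smaller gains. Interpret the gain from its 95% confidence interval together with the observed QDRS accuracy; D.8.a already plans bootstrap intervals for the differences. Draw no conclusion about limits of EHRs when that interval includes clinically relevant gains.

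**Cost.** Wording in two sections. The stated power for the QDRS comparison becomes less favourable. No extra patients and no change to the analysis.

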#### **D.7.b. Incidence of ADRD for the pragmatic cluster-randomized comparative effectiveness clinical trials:**

For the two pragmatic trials and using similar approach from previous studies, we will use data captured by the EHR to assess for two outcomes. The primary outcome measure will be any new ADRD case identified (documented in the EHR) within 12 months of the Annual Wellness Visit (index visit). The secondary outcome measures will be any services related to cognitive diagnostic assessment in the post Annual Wellness Visit (index) period that providers may order to diagnose or exclude ADRD. Specifically, the metrics

of diagnostic assessment will be evaluated as proportions of patients with a record of 1 or more of:

- Laboratory tests for TSH, serum B12, folate, or syphilis; individually or combined at any point during the 90 days after index
- Neuropsychological testing, including testing by psychologist or physician, technician administrator, computer, or other providers during the 12 months after index date
- Brain imaging testing (computed tomography, magnetic resonance imaging, positron emission tomography, magnetic resonance angiogram) of the head and neck, brain, or skull during the 12 months after index date
- Medications approved for management of ADRD (cholinesterase inhibitors, memantine) during the 12 months after index date

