Because the other studies are two separate pragmatic clinical trials, participants will be cluster-randomized to three different arms. This approach ensures that rigorous testing of the outcomes (incident ADRD detection and acceptance of subsequent diagnostic assessments) is not contaminated by the other screening approaches in other arms of interest. In addition, the 400 patients in study 1 will be excluded from the two pragmatic trials to avoid contamination. The total sample for each pragmatic trial will be slightly over 2,600, if each of enrolled practice screen conservatively 175 patients per year for a total of two years of screening. Alternatively, the total sample size for each trial will be 3,600, if we recruit, as we have in past trials, 200 patients per clinic. The table below shows the power for comparing ADRD incidence and acceptance rates between two different arms under the conservative and historical recruitment scenarios. Calculations were based on using nonlinear mixed models to compare two independent proportions, assuming cluster randomization (i.e., level-2 randomization) and the

ICC is 0.01. The “AWV alone” arm is expected to have ADRD incidence of 6% and acceptance rate of 44%. The table shows that power will exceed 80% to detect ADRD incidence of 6% vs 13%, even under conservative recruitment projections, and power for comparing acceptance rates will be 99%.

Outcome	Conservative recruitment* (N = 2,600)	Projected (feasible historically) recruitment* (N = 3,600)
ADRD incidence 6% vs 13%	86%	89%
Acceptance 44% vs 66%	99%	99%

\*Conservative recruitment = Total of 2,600 patients with 866 patients and 5 clusters per each of 3 arms; power for pairwise comparisons based on 1,732 patients with 866 patients and 5 clusters per each of 2 arms, and M = 173.2 patients per cluster. Historical recruitment = Total of 3,600 patients with 1,200 patients and 5 clusters per each of 3 arms; power for pairwise comparisons based on 2,400 patients with 1,200 patients and 5 clusters per each of 2 arms, and M = 240 patients per cluster.

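### The per-practice accrual in D.8.c does not produce the cohorts of 2,600 and 3,600 used for power, and D.7.b does not fix one index visit per patient

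*Combined protocol and SAP*

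**What the plan says.** **Accrual and cohort size (D.8.c).** The conservative scenario puts each pragmatic trial at a little over 2,600 patients, "if each of enrolled practice screen conservatively 175 patients per year for a total of two years of screening". The alternative reads: "the total sample size for each trial will be 3,600, if we recruit, as we have in past trials, 200 patients per clinic". The footnote to the power table gives the inputs actually used. For the conservative case it states "Total of 2,600 patients with 866 patients and 5 clusters per each of 3 arms", with M = 173.2 per cluster. The historical case has 3,600 patients, again 5 clusters in each of 3 arms, with M = 240. The ICC is 0.01, and D.8.c adds "All calculations assume two-sided tests and alpha = 0.05". Tabulated power for 6% versus 13% incidence is 86% and 89%.

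**Number of practices.** D.5 says "Each pragmatic trial will randomize primary care practices into one of three approaches for early detection of ADRD at (1:1:1) ratio". The footnote implies 15 practices per trial. D.2 lists 10 practices in each health system. D.10 speaks of 15 practices recruited from the two sites.

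**Index visit.** D.7.b defines the primary outcome as "any new ADRD case identified (documented in the EHR) within 12 months of the Annual Wellness Visit (index visit"). D.4 deploys the tools at the AWV and also at other primary care or geriatric visits. D.8.b handles correlation with random effects for patients within clinics.

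**The concern.** The power statement for each pragmatic trial rests on a chain: practices, patients per practice, total, cluster size, power. The first links do not connect to the later ones, so a reader cannot tell which accrual target each practice must meet, or whether 2,600 and 3,600 are one-year counts, two-year counts or something else. Recruitment monitoring and any later judgement that a trial reached its planned size depend on that.

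The index visit is a related but separate gap. An annual visit offered over two years of screening can occur twice for the same patient, and no rule says which visit starts the 12-month window or that a patient enters once. Take a patient with AWVs in months 3 and 15 and a diagnosis in month 20. The diagnosis falls 17 months after the first visit (not a case) and 5 months after the second (a case). Two people extracting EHR data under the same protocol could classify that patient differently on the primary outcome. Settling the rule after retrieval would be a data-dependent choice.

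**Working it through.** **Inputs.** From D.8.c: two-sided alpha 0.05, rates 0.06 and 0.13, ICC 0.01, 5 clusters in each of 3 arms, M = 173.2 or 240, and accrual of 175 per practice per year for two years or 200 per clinic. From D.2 and D.10: the other practice counts.

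**Formulas.** Design effect DE = 1 + (M − 1) × 0.01. Effective size per arm n* = 5M / DE. Power = Φ[(0.07 − 1.96 × se0) / se1], where se0 = √[2 × 0.095 × 0.905 / n*] and se1 = √[(0.06 × 0.94 + 0.13 × 0.87) / n*] = √(0.1695 / n*). These are normal-approximation figures, kept so that they compare directly with the plan's table.

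**Step 1: reproduce the table from its footnote.**
- M = 173.2: DE = 2.722; n* = 866 / 2.722 = 318.1; (0.07 − 1.96 × 0.02325) / 0.02308 = 1.06; power 85.5% (85.8% with unpooled variance). Stated: 86%.
- M = 240: DE = 3.39; n* = 1,200 / 3.39 = 354.0; (0.07 − 1.96 × 0.02204) / 0.02188 = 1.22; power 89.0% (89.2% unpooled). Stated: 89%.

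The table is correct for those inputs.

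**Step 2: totals from the accrual text at 15 practices.**
- 15 × 175 × 2 = 5,250, against a little over 2,600. One year alone is 15 × 175 = 2,625.
- 15 × 200 = 3,000, against 3,600. Reaching 3,600 takes 3,600 / 15 = 240 per practice, or 3,600 / 200 = 18 practices.

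**Step 3: power at the accrual as written, 5 clusters per arm.**
- 350 per practice: DE = 4.49; n* = 1,750 / 4.49 = 389.8; power 91.7%, if all 5,250 are distinct patients.
- 200 per practice: DE = 2.99; n* = 1,000 / 2.99 = 334.4; power 87.2%.

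If some patients seen in year one return in year two, 5,250 counts visits. Distinct patients would be 5,250 with no returners, about 3,938 if half return (5,250 − 0.5 × 2,625) and 2,625 if all do. The documents give no return share, so these are illustrations.

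**Step 4: can another practice count rescue the totals?**

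| Practices per trial | Source | 350 per practice | 200 per practice |
|---|---|---|---|
| 15 | D.8.c footnote | 5,250 | 3,000 |
| 10 | D.2, one health system | 3,500 | 2,000 |
| 7.5 | D.10's 15 split over two trials | 2,625 | 1,500 |
| 18 | needed for 3,600 at 200 | 6,300 | 3,600 |

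No row gives both 2,600 and 3,600. With 10 practices per trial, treated as 3.33 per arm, power is 77.8% at 3,500 patients (n* = 259.8) and 71.4% at 2,000 (n* = 223.0).

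**Step 5: index visit, sections side by side.** D.7.b refers to the AWV as the index visit without saying first, latest or any. D.8.c plans two years of screening. D.8.b has no patient-level term, so repeat records from one patient would be unmodelled if they entered. The cohort in C.2 that underlies the 6% benchmark (6.16% in the AWV group) is described with a single index visit, 12 months of follow-up and no earlier ADRD.

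**The case against.** The best defence is that the power calculation itself is sound. It reproduces from the footnote, counts patients rather than visits, and at 15 practices every figure above stays over 80%. That stands: the fault lies in the link from accrual to cohort, not in the power formula, and at 15 practices it moves nominal power by only a few points, up in one scenario and down in the other.

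On the index visit, D.7.b uses the singular, D.8.c counts patients, and D.7.b says it follows an approach from earlier studies, one of which is the single-index cohort in C.2. One entry per patient is therefore the natural reading. That also largely stands: double records are possible under the text but not shown to be intended. It does not supply the missing rule on which AWV counts.

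Two stronger readings are tempting and should be resisted.

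- A reader might infer that 5,250 and 2,625 agree only if the same patients come back in year two, so that the plan must be counting returners. One year's accrual at 15 practices also gives 2,625, and so does splitting 15 practices over two trials at 350 each, although the latter conflicts with the footnote's 5 clusters per arm.
- A reader might infer that two 12-month windows would raise the incidence in both arms well above 6% and 13%. That needs a return share the documents do not give and an undiminished 13% in year two, after first-year detections have left the pool. It also needs two complete windows per patient. The D.10 text recruits practices at the start of Year 3 and retrieves data in Year 4, at most about 24 months, which leaves essentially no room for two. The timetable grid appears to place retrieval in Year 5, which would allow it only for early entrants.

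**Conclusion.** The accrual statements and the cohort sizes in D.8.c contradict each other. At the footnote's 15 practices per trial, the text yields 5,250 and 3,000 where the table uses 2,600 and 3,600. Power for 6% versus 13% at the stated accrual is about 92% and 87%, rather than 86% and 89%. These figures assume ICC 0.01, five equal clusters per arm and, for the 92%, no repeat patients. The change in power is modest at 15 practices. The practice count matters more: if only 10 per trial are available, power is roughly 71% to 78%, below the 80% that D.8.c says will be exceeded.

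The index-visit gap is real but smaller. The documents do not show that patients will be counted twice, and no size can be put on any resulting bias. They simply leave the choice of index open for a patient with two AWVs. Both parts should be corrected before EHR data are retrieved.

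**What to change.** 1. Reconcile the number of practices per trial across D.2, D.8.c and D.10.
2. Restate per-practice accrual, N, M and power in D.8.c so that they agree. At 15 per trial, the conservative case is either 175 patients per practice in total (2,625, about 86%) or 350 (5,250, about 92% if all are distinct). The historical case is either 240 per practice (3,600, 89%) or 200 per practice (3,000, about 87%). If the count is 10 per trial, recompute power and report it.
3. In D.7.b, define the index as the patient's first AWV after the practice's go-live, with each patient entered once and later AWVs not re-indexed. This matches the single-index cohort behind the 6% benchmark.
4. State how patients screened at the other visits allowed in D.4 are handled, including those screened before their first AWV.

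The cost is protocol wording and a few restated figures, with no new data collection. The downside is that the historical-scenario power becomes slightly less favourable if 200 per clinic is the true rate.

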Potential problems & alternative strategies: The distributional assumptions for the binary outcomes are minimal, which will decrease the need to consider alternative analytic methods and models. However, to ensure the analytic methods appropriately account for the clustering effect when estimating standard errors and p-values, we will perform bootstrap estimation (i.e., using 1,000 datasets resampled with replacement at the person level) of the standard errors and confidence intervals surrounding the estimated values for AUC and % accuracy, and the estimated values for the difference in these values between screening approaches. In addition, if missing data occur, we will impute data using the simulation-based “Multiple Imputation” method, in which multiple complete datasets with plausible values for missing data are generated using model-based prediction, and analytic results from imputed datasets are aggregated to calculate appropriate standard errors and p-values in the presence of imputed data. We will use 100 imputed datasets, even though 10 to 50 are considered sufficient. Inclusion of potential auxiliary variables in the imputation model will be considered. A sensitivity analysis will be performed using participants with complete data.

**D.8.b. Primary Aim 2:** Evaluate the practical utility and effect of the PDM, and the combined methods in improving the annual rate of new documented ADRD diagnosis in primary care practices.

For Primary Hypothesis 1, three pragmatic screening approaches (AWV alone, AWV + PDM, and AWV + PDM + QDRS) will be compared on the annual incidence rate of EHR documented ADRD using nonlinear mixed models to account for clinic-clustered data. In the two pragmatic trials, different patients are randomized (via their clinics) to each of the 3 arms, making the outcomes independent between the three screening approaches; however, data will still be correlated for Aim 2 due to clustering of patients within clinics, which will be handled by random effects in the mixed models. We hypothesize the incidence rate will be 6% using AWV alone and 13% with the screening approach that combines AWV + PDM + QDRS. Incidence rates for all arms, including for AWV + PDM, will be calculated along with their 95% confidence interval.

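### The 86% and 89% power for 6% versus 13% rest on a 1.96 cut-off; at about a 5% level with 5 practices per arm, two-arm power is about 74–81% and 78–83%

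*Combined protocol and SAP*

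**What the plan says.** D.8.c sets two-sided tests at alpha 0.05 and uses PASS. For the pragmatic trials it states: "Calculations were based on using nonlinear mixed models to compare two independent proportions", with randomization by practice and ICC 0.01. The table gives 86% power (2,600 patients) and 89% (3,600 patients) for 6% versus 13%. The footnote fixes the basis of the conservative figure: "power for pairwise comparisons based on 1,732 patients with 866 patients and 5 clusters per each of 2 arms", with 173.2 patients per practice. The historical figure uses 1,200 patients and 5 practices per arm, 240 per practice. The text concludes: "The table shows that power will exceed 80% to detect ADRD incidence of 6% vs 13%, even under conservative recruitment projections".

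D.8.b describes the analysis: "three pragmatic screening approaches (AWV alone, AWV + PDM, and AWV + PDM + QDRS) will be compared" on annual incidence "using nonlinear mixed models to account for clinic-clustered data". Correlation within clinics is something "which will be handled by random effects in the mixed models". Neither section names a reference distribution, degrees of freedom or small-sample correction. For potential problems in Aim 2 the plan says "Same as those described for Aim 1 above", and the clustering safeguard given there is a bootstrap "using 1,000 datasets resampled with replacement at the person level".

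**The concern.** With 5 practices per arm, the precision of the treatment contrast is governed by a between-practice variance estimated from 10 practices, or 15 if all three arms are modelled. A critical value of 1.96 ignores the uncertainty in that estimate. If it is used in the analysis, the false-positive rate exceeds 5%. If a valid small-sample test is used instead, power is below the tabulated figure. The person-level bootstrap does not help, because it never resamples practices. At stake is the primary hypothesis of both pragmatic trials: either inflated type I error, or a choice of test made after the data are seen.

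**Working it through.** **Inputs (D.8.c).** Incidence 6% and 13%; ICC 0.01; 5 practices per arm; M = 173.2 or 240; two-sided 0.05; inflation factor 1 + (M − 1) × ICC. That formula is stated for study 1 and is applied here to the pragmatic trials.

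**1. Reproduce the plan.** Inflation factor: 1 + 172.2 × 0.01 = 2.722, and 1 + 239 × 0.01 = 3.39. Variance term: 0.06 × 0.94 + 0.13 × 0.87 = 0.1695.

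- Conservative: SE = √(2.722/866 × 0.1695) = 0.02308; 0.07/0.02308 = 3.03
- Historical: SE = √(3.39/1,200 × 0.1695) = 0.02188; 0.07/0.02188 = 3.20

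With a normal reference, power = Φ(3.03 − 1.96) = 85.8% and Φ(3.20 − 1.96) = 89.2%. Both table entries are matched.

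**2. Change only the reference distribution.** Two arms and 10 practices leave 10 − 2 = 8 degrees of freedom, with critical value 2.306. The noncentral t gives 75.7% and 80.0%, about 9–10 points below the table. The table therefore used 1.96; this is inferred from the match, not stated in the plan.

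**3. Type I error at 1.96.** A t statistic on 8 df exceeds 1.96 in absolute value with probability 8.6%. In simulation (beta-binomial practices, ICC 0.01, 5 per arm), a practice-level statistic gives about 8.4%. A maximum-likelihood random-intercept logistic Wald test gives about 10–12%.

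**4. Two-arm power at about 5%, by simulation under the same model.**

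| Test | Size | Power, conservative / historical |
|---|---|---|
| Practice-level t, 8 df | 4.8–5.0% | 76.5% / 80.6% |
| Random-intercept logistic, restricted pseudo-likelihood, between-practice t or Kenward-Roger | 4.4–4.8% | 76.4–76.5% / 80.7% |
| Exact permutation over 252 allocations | 3.9–4.2% | 74% / 78% |
| Maximum-likelihood logistic, critical value calibrated by simulation | 5% by construction | 79–81% / 80–83% |

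A plain t critical value on the maximum-likelihood fit is not enough: its size is about 6–7%.

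**5. Three arms.** The plan gives no incidence for AWV + PDM, so 6%, 9.5% and 13% are assumed. The pooled-variance practice-level t on 12 df, with 6% in both compared arms and M = 173, has size 4.9%, 3.5% and 2.7% respectively. With the critical value reset to give 5% in each setting, its power is about 83–85% conservative and 87–88% historical. With both compared arms at 13% and the third at 6%, the same test is liberal (7.1%).

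The restricted pseudo-likelihood logistic model on 12 df has power of about 81% / 85% with the third arm at 9.5%. Its size is 4.7–4.9% when all arms share one incidence, but 5.9–6.7% with the third arm at 13% and the compared arms at 6%.

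**The case against.** The strongest reply is that D.8.b describes a three-arm comparison, and a three-arm model borrows variance information from 15 practices. This stands in part: such a model can give roughly 81–85% under conservative recruitment. But D.8.c states its power on two arms, and the three-arm result depends on an incidence that the plan does not supply.

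A reader might instead infer that the three-arm analysis also fails, because the closed-form noncentral t on 12 df gives 79.5%. That does not follow. Where the third arm has the higher incidence, the pooled-variance test is undersized, and its power at a true 5% level is above 80%.

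It can also be said that the 1.96 is inferred and that the plan never commits the analysis to it. That is correct. The inference concerns how the table was computed; for the analysis, the documented gap is that no reference distribution is named.

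Finally, other inputs are unsettled. D.8.c mentions 175 patients per year for two years, or 350 per practice, which would give 83.5% on 8 df. D.2 lists 10 practices per health system, and D.10 has 15 from the two sites together, against the 15 per trial that the table needs. These could move power either way and must be reconciled, but the table as written uses 173.2 and 240 patients and 5 practices per arm.

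**Conclusion.** The concern holds on the plan's own two-arm basis. The arithmetic is not wrong: 86% and 89% follow from a large-sample formula. They are not delivered at the stated alpha with 5 practices per arm. For tests on 8 df the overstatement is about 9–10 points (conservative) and 8–9 points (historical); it is 11–12 points for permutation and about 5–9 points for the calibrated maximum-likelihood model.

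A reader might infer that the trials are underpowered. The documents do not support that. Historical recruitment stays at about 80% or above except with permutation, some analyses keep conservative power just over 80%, and the acceptance comparison is unaffected (99.9% on 8 df at the plan's M). What fails is the assurance of more than 80% even under conservative recruitment.

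The figures assume ICC 0.01 and beta-binomial variation. The margin is thin: at M = 173.2, power falls to 80% at ICC 0.0127 with 1.96, but at 0.0084 on 8 df. With logit-normal variation (SD 0.36) as a sensitivity case, conservative power at about 5% is 70–79%.

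**What to change.** **D.8.b.** For AWV + PDM + QDRS versus AWV alone, name one test that holds two-sided 0.05 with 5 practices per arm, and say whether it uses two-arm or three-arm data. The closest checked match to the planned model is the two-arm random-intercept logistic model fitted by restricted pseudo-likelihood, with Kenward-Roger or a between-practice t on 8 df. If a three-arm model is preferred, check its size by simulation under unequal third-arm incidence and do not rely on plain 12 df.

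**D.8.c.** Replace 86% and 89% with the power of the named test (about 76% and 81% for the two-arm example). State any third-arm incidence assumed. Remove or qualify the claim about conservative recruitment.

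**Cost.** One test specification, one short simulation, two restated figures and one reworded sentence. The downside is a less favourable stated power.
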